## Section 7.0 Study Parameters

### 7.1 Laboratory/imaging Studies:

Parameter	Baseline	Pre- and post-SRT therapy	Post-Treatment Follow-up
History	X	X b	a
Physical examination	X	X b	a
Weight	X	X	a
Vital signs	X	X	a
Performance status (Karnofsky)	X	X	a
CBC, differential, platelet count	X	X Post- SRT	a
Comprehensive metabolic panel (including bilirubin, alk phos, AST, ALT, )	X	X Post- SRT	a

Fill out pain assessment card	X	X Post-SRT	a
AFP	X	X post-SRT	a
PT, PTT, INR	X	X Post-SRT	a
CT	X	X simulation	
MRI	X	X Post-SRT	a
Serum pregnancy test	prn		

*a - will be done at one month and 3 months after the completion of SRT*

*b – A brief physical exam and history will be performed*

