## Section 10.0 Statistical considerations

### 10.1 Trial Design

This phase I trial will determine safety, dose-limiting toxicities (DLT) and maximum tolerable dose (MTD) of SRT for HCC. Although unacceptable toxicity is unlikely, four dose levels (40, 50, 60, 70 Gy in 5 fractions) will be evaluated in a cohort escalation design of 3-6 patients. At the MTD, 10 additional patients will be enrolled to generate pilot data on radiologic response and to evaluate further toxicity. Patients will start at dose level II (50 Gy at 5 fractions).

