#### Endpoints

Toxicity will be graded by NCI Common Toxicity Criteria (CTC Version 3.0). Due to delayed toxicities attributable to radiotherapy, all toxicities observed within 1 month after SRT will be scored. DLT is defined as any of following toxicities, that is possibly, probably or definitely related to SRT occurring within 30 days from the start of treatment:

- a) grade 4 or 5 hepatic
- b) grade 4 or 5 gastrointestinal
- c) grade 4 or 5 thrombocytopenia
- d) grade 4 hepatic liver enzyme elevations persisting for  $\geq 5$  days
- e) any adverse event requiring interruption of therapy by  $\geq 2$  weeks (14 calendar days). This does not include patient desire to discontinue therapy. It does include failure for thrombocytopenia to improve to a level of 80 requiring interruption of therapy.
- f) Any grade 5 treatment-related adverse event

The MTD of SRT is defined as the highest dose level at which no greater than 2 DLT is observed in 6 patients.

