## Appendix II

### Schedule of Activity

	Screening/Baseline	Liver Marker Implant Procedure	1-7 Days Post Implant	SRT planning,	Start SRT	End SRT	1 month Post SRT	3 Months Post SRT
History & Physical	x		x	x	x	x	x	x
CT abdomen/pelvis	x	x		x				
MRI abdomen/pelvis	x			x				x
biopsy	x							
Inclusion/Exclusion	x							
Informed consent	x							
CT or U/S guided marker implant		x						
AFP	x			x			x	x
CBC with diff	x		x	x			x	x
INR	x							
complete chemistry pannel	x		x	x			x	x
Chest X-ray or Chest CT	x							
Record adverse events		x	x	x	x	x	x	x

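### Appendix II schedules no liver chemistry inside the 30-day DLT window and conflicts with 7.1, so a purely laboratory liver DLT can go undetected

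*Combined protocol and SAP*

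**What the plan says.** **DLT definition (10.1, Endpoints).** Item (a) is "grade 4 or 5 hepatic" toxicity. Item (d) is "grade 4 hepatic liver enzyme elevations persisting for" 5 days or more. Both must be at least possibly related to SRT and "occurring within 30 days from the start of treatment". The sentence just before the definition uses another clock: "all toxicities observed within 1 month after SRT will be scored".

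**Schedule in 7.1.** The row that begins "Comprehensive metabolic panel (including bilirubin, alk phos, AST, ALT" is marked at baseline, once post-SRT with no day given, and at follow-up. The footnote says follow-up tests "will be done at one month and 3 months after the completion of SRT". PT, PTT and INR follow the same pattern.

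**Schedule in Appendix II (named in 4.6).** The row "complete chemistry pannel" is marked at screening, 1-7 days after implant, SRT planning, and 1 and 3 months after SRT. The Start SRT and End SRT cells are empty. INR is marked at screening only.

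**Other relevant text.**
- 9.3 has its own DLT rule: any CTCAE toxicity of grade 4 or above, with no persistence requirement and no day limit.
- 5.2.2 and 9.3 hold the next dose level for four weeks after SRT. The escalation rules in 10.1 ask for at least 1 month of observation.
- 9.3 finds adverse events through patient reports and physical examination, records onset and resolution dates, and passes outside laboratory results to the research nurse. It sets no frequency for blood tests.
- 5.3 says nothing is done solely for research.

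**The concern.** The liver is the first organ named in the primary objective, and the trial admits Child-Pugh class B patients. Escalation depends on counting DLTs, and an enzyme rise is seen only if blood is drawn. A site working from Appendix II could close a patient's DLT window with no post-treatment bilirubin, AST, ALT or INR on file and still record no hepatic DLT.

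The error runs one way. A missed event can only lower the DLT count, which favours escalation and a higher declared MTD. The operating characteristics in 10.3 also take for granted that every DLT is seen.

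**Working it through.** **1. Reproduce the plan's own figures (10.3).** Take six patients, no escalation with 2 or more DLTs, and full detection.
- True rate 35%: 1 − [0.65⁶ + 6 × 0.35 × 0.65⁵] = 0.681, against at least 68% stated.
- True rate 20%: 0.8⁶ + 6 × 0.2 × 0.8⁵ = 0.655, against 66% stated.

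Both reproduce as a fixed six-patient calculation. The rule written in 10.1 for levels II and III is sequential: escalate after 0/3, or after 1/3 followed by 0/3. Its probability is P(escalate) = (1−p)³ + 3p(1−p)² × (1−p)³. This gives 0.396 at p = 0.35 and 0.709 at p = 0.20.

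**2. Date the 1-month panel.** There are five fractions (10.1) within 2 weeks (abstract, 5.2.2), so the last falls at about day 5 to 14. No visit windows are given; I take a month as 28 to 31 days.
- Earliest: 5 + 28 = day 33.
- Latest: 14 + 31 = day 45.

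To fall by day 30, the panel would have to be drawn no more than 30 − 5 = 25 days after the last fraction, or 30 − 14 = 16 days if SRT takes the full two weeks.

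**3. Count scheduled liver panels from the start of SRT.** The undated post-SRT panel in 7.1 is assumed to be drawn near the end of SRT.

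| Clock | Appendix II | 7.1 |
|---|---|---|
| 30 days from start (DLT definition) | 0 | 1 |
| 1 month after SRT (preceding sentence) | 1, at the edge | 2, about 4 weeks apart |

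Item (d) needs at least two dated values 5 or more days apart. On the 30-day clock neither schedule supplies them. On the longer clock only 7.1 does, and a rise lasting between 5 days and about 4 weeks could have resolved by the second value.

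**4. Effect of missed events.** Let m be the share of true DLTs that are laboratory-only and missed. The documents give no value for m, so these are assumed shares. The observed rate is p(1−m).

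| m | Observed rate, true 35% | P(escalate), 10.1 rule | P(escalate), fixed six as in 10.3 | P(escalate), 10.1 rule, true 20% |
|---|---|---|---|---|
| 0% | 0.35 | 39.6% | 31.9% | 70.9% |
| 25% | 0.2625 | 57.3% | 50.5% | 81.4% |
| 50% | 0.175 | 76.2% | 71.7% | 90.6% |
| 75% | 0.0875 | 92.6% | 90.9% | 97.3% |

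**The case against.** **The 30-day window is not the only clock.** 10.1 also scores toxicity up to 1 month after SRT, and 5.2.2 and 9.3 make escalation wait four weeks after SRT. On those clocks the 1-month panel lands close to the decision. This stands as a reason to reconcile the text. It does not remove the problem: the definition that labels an event a DLT uses 30 days from the start, and a four-week wait (28 days) can end up to 3 days before a 1-month visit at 31 days.

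**One grade 4 value may be enough.** Under 9.3 any grade 4 toxicity is a DLT, and item (a) has no persistence clause. So a reader should not infer that failing to prove 5-day persistence always loses the event. This also stands, but a single value still has to be drawn, and Appendix II schedules none in the window.

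**Persistence is partly covered.** 9.3 requires onset and resolution dates, so a recorded grade 4 value should be followed up, and a visit table does not forbid repeats. What remains is mainly first detection, together with the absence of any stated repeat after an abnormal value.

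**7.1 already requires a post-SRT panel.** The count of zero applies only where a site works from Appendix II. That is correct, but 4.6 names Appendix II as the study schedule, and nothing says which prevails.

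**Other routes exist.** Clinically evident liver toxicity meets item (a) without a scheduled panel, and outside laboratory results may reveal others. So the documents do not support the inference that liver DLTs in general would go unseen. Only purely biochemical ones are exposed, and some of those may be caught.

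**Conclusion.** The concern holds in a limited form. The two schedules conflict on chemistry and INR, and the one named in 4.6 provides no liver panel between SRT planning and about day 33 to 45, while the DLT window in 10.1 closes at day 30. Neither schedule provides two in-window values for item (d). Laboratory-only liver DLTs can therefore go undetected, with a bias towards escalation.

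The direction is firm but the size is not. A reader might take 76.2% as an estimate of this trial's escalation probability. It is not: it follows from assuming that half of all DLTs are missed, and the assumed share alone moves the result from 39.6% to 92.6%. The dating rests on SRT ending at day 5 to 14 and on nominal 28- to 31-day months.

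This is a should-fix. A stronger rating would need the safeguards in 7.1 and 9.3 to be absent, and they are only inconsistent with the rest.

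**What to change.** 1. Correct Appendix II so that it carries the post-SRT chemistry panel and INR, and the 1- and 3-month INR, that 7.1 already lists.
2. Reconcile the clocks (30 days from the start and 1 month after SRT in 10.1; four weeks after SRT in 5.2.2 and 9.3) so that the panel used for the escalation decision lies inside the DLT window. Without this, a grade 4 value at the 1-month visit would still fall outside the 10.1 definition.
3. Require the scheduled post-SRT panels on file before a patient is counted as having no DLT. Any patient with a DLT or who dies counts regardless of missing panels. The condition should not be written as a test of evaluability: patients who die early, or are removed for a DLT under 5.6.3, may never have a 1-month panel, and excluding them would add to the same bias.
4. Reconcile the any-grade-4 rule in 9.3 with item (d) in 10.1. If persistence is kept, state how it is determined from dated values.

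The cost is one table correction and a few sentences in 9.3 and 10.1; the added draws are already in 7.1. The downside is that a few more hepatic DLTs may be scored and escalation waits for the 1-month panel. A rise that begins and resolves between scheduled draws would still be missed.

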## 9.3 Data and Safety Monitoring Plan

This protocol will comply with monitoring and adverse event reporting requirements of the UNMC/Eppley Cancer Center Data Monitoring Plan. All research data will be stored in the case report forms in a locked file cabinet. These forms are available only to the investigators, his/her designee (i.e., the study coordinator), the UNMC Eppley Cancer Center Scientific Review Committee (SRC), and representatives of the Institutional Review Board at the University of Nebraska Medical Center. Any information obtained during this study which could identify the subject will be kept strictly confidential and will be identified by code numbers rather than the patient's name. The data safety plan also includes: Weekly review of all patients on study by the investigators. All adverse events will be reported to the PRMS Internal Audit Committee for audit by a clinician not involved with the clinical trial.

All patients will be closely followed for toxicity. Toxicity will be assessed using the revised NCI Common Toxicity Criteria (version 3.0) retrieved from the National Cancer Institute, Cancer Therapy Evaluation Program web site: ([ctepcancer.gov/forms/CTCAEv3.pdf](http://ctepcancer.gov/forms/CTCAEv3.pdf)). Therapy will be discontinued at any time due to the development of unacceptable toxicity. If a Grade 1 or 2 or 3 toxicity develops, the investigator may elect to continue the treatment with careful monitoring. Any grade 4 or greater toxicity according to CTCAE v3 will constitute a DLT. 1) SRT dose escalation will be stopped if 2 patients at a given dose level experience a DLT. If one patient has a DLT, then an additional five patients will be evaluated at the same dose level. 2) Implantation of a liver marker will be stopped if 2 patients experience implant-related-adverse events which do not response to medical or surgical management.

Therapy will be discontinued at any time due to the development of unacceptable toxicity. If, at any time, the data suggest a significant hazard to further dose escalation, regardless of whether the formal stopping rules are satisfied, dose escalation will be halted pending a review of all data. There will be a four week waiting period after the last patient in each cohort completes radiation therapy for toxicity evaluation between dose levels.

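### Sections 9.3 and 10.1 define dose-limiting toxicity differently for the same escalation decision, and neither definition contains the other

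*Combined protocol and SAP*

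**What the plan says.** Section 9.3 (Data and Safety Monitoring Plan) states: "Any grade 4 or greater toxicity according to CTCAE v3 will constitute a DLT". The consequences follow at once: "SRT dose escalation will be stopped if 2 patients at a given dose level experience a DLT", and "If one patient has a DLT, then an additional five patients will be evaluated at the same dose level". No organ list, relation to treatment or time limit is attached. The same section adds: "There will be a four week waiting period after the last patient in each cohort completes radiation therapy". It also allows escalation to be halted for a significant hazard even when the formal rules are not met.

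Section 10.1 (Endpoints) gives delayed radiation toxicity as the reason why "all toxicities observed within 1 month after SRT will be scored". It then defines a DLT as a listed event that is "possibly, probably or definitely related to SRT occurring within 30 days from the start of treatment". The list is:

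- (a) "grade 4 or 5 hepatic";
- (b) gastrointestinal toxicity of the same grades;
- (c) thrombocytopenia of the same grades;
- (d) "grade 4 hepatic liver enzyme elevations persisting for" 5 days or more;
- (e) an adverse event, of whatever grade, that interrupts therapy for 2 weeks or more;
- (f) any treatment-related grade 5 event.

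The Dose-escalation Rules, also in 10.1, act on the DLT count and add three patients after 1/3, not five.

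Section 5.6.3, in the criteria for taking a patient off study, refers to DLT as defined at 10.1. Section 1.1.1.1 names liver, right kidney and small bowel as the organs whose toxicity is to be recorded for the primary objective.

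**The concern.** The DLT count decides whether a cohort is expanded, whether the dose goes up, and which level is called the maximum tolerated dose. Cohorts hold 3 to 6 patients, so a single event can settle the matter. If two sections count different events, two careful people with the same patient data can reach different dose decisions, each in line with the plan.

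Two features make this more than untidy wording. Kidney is one of the three organs in the primary safety objective, yet 10.1 has no kidney item. And 10.1 recognises that radiation toxicity can be delayed, then closes its DLT window before the observation period planned to detect such toxicity has ended.

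**Working it through.** **1. The plan's own figures.** Section 10.3 matches a rule of escalating on at most 1 DLT in 6:

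- True rate 35%: P(not escalating) = 1 − [0.65^6 + 6 × 0.35 × 0.65^5] = 1 − 0.319 = 0.681 (stated: at least 68%).
- True rate 20%: P(escalating) = 0.80^6 + 6 × 0.20 × 0.80^5 = 0.262 + 0.393 = 0.655 (stated: 66%).

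Both take a DLT rate as given. They do not say which definition that rate refers to, so they cannot settle the question.

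**2. The two definitions side by side.** Except on day 35, each event is taken to fall inside the first 30 days.

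| Event | 9.3 | 10.1 |
|---|---|---|
| Related grade 4 kidney toxicity, no 2-week interruption | DLT | Not a DLT (not listed) |
| The same, with therapy interrupted for 2 weeks or more | DLT | DLT, item (e) |
| Related grade 4 gastrointestinal toxicity first seen on day 35 | DLT | Not a DLT (outside window) |
| Unrelated grade 4 event | DLT (no attribution condition) | Not a DLT |
| Related grade 1–3 event that interrupts therapy for 2 weeks or more | Not a DLT | DLT, item (e) |
| Related grade 4 enzyme rise lasting under 5 days | DLT | Unclear: no under (d), yes if (a) includes enzymes |

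Rows 1, 3 and 4 count under 9.3 only, and row 5 under 10.1 only. Neither set contains the other.

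**3. The window.** Inputs are five fractions (10.1), given within 2 weeks (5.2.2), a four-week wait after radiotherapy (9.3), and a window of 30 days from start (10.1). Take the first fraction as day 0.

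- Last fraction: day 4 (five consecutive days) to day 14.
- End of wait: 4 + 28 = day 32, to 14 + 28 = day 42.
- Part of the wait outside the 10.1 window: 32 − 30 = 2 days, to 42 − 30 = 12 days.

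The wait runs from when the last patient in the cohort finishes, so these figures are for that patient. Patients who finished earlier are observed for longer past their own day 30. If the wait is instead 1 month, taken as 30 days, the gap is 34 − 30 = 4 to 44 − 30 = 14 days.

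**4. One patient.** Under 10.1, 0/3 escalates. One reclassified patient makes it 1/3, which calls for three more patients under 10.1 and five more under 9.3. Likewise 1/6 allows escalation under 10.1 (or, at level IV, declares the maximum tolerated dose), while 2/6 stops escalation under both sections. Because of item (e), the reclassification can run in either direction.

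**The case against.** The strongest reply is that the documents already lean one way. Section 5.6.3 places the definition of DLT in 10.1, and the detailed escalation rules follow directly on it, so 9.3 can be read as loose monitoring-plan wording. That much stands: a reader might infer that nothing in the plan points to either section, and that would be too strong. But 5.6.3 concerns removing a patient, while 9.3 sets its own definition beside its own stopping rule.

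The hazard clause in 9.3 is also a genuine safeguard for late or unlisted grade 4 events. It is discretionary, however, and does not say what enters the count.

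The word toxicity in 9.3 might be taken to imply a relation to treatment. On that reading the unrelated-event row drops out, but the kidney, late-event and item (e) rows remain.

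Four further inferences are tempting but not supported:

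- *Section 9.3 is simply the stricter rule, so following it is safe.* Item (e) counts events that 9.3 does not.
- *Short enzyme rises are definitely treated differently.* That holds only if item (a) excludes enzymes, and the text does not say.
- *The conflict shifts the chance of escalating by a stated amount.* The documents give no rate for events on which the sections disagree, and those events go both ways. Nor does 9.3 give a first-cohort size; 5.2.2 speaks of groups of 5.
- *Enzyme rises would first be found after the 10.1 window.* Appendix II marks no chemistry panel between planning and 1 month after SRT, but section 7.1 lists a post-SRT panel without a day, which may fall inside the window.

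**Conclusion.** The inconsistency is real and should be corrected. It concerns which toxicities count, whether they must be related to SRT, and when they must occur. The case rests on the text, not on a probability. Its size is one patient, enough to turn 0/3 into 1/3 or 1/6 into 2/6, together with a stretch of 2 to 12 days at the end of the wait in which no newly occurring event can be a 10.1 DLT. The day count assumes that day 0 is the first fraction, that the last fraction falls on day 4 to 14, and that the wait is 28 days. The enzyme-duration question is a secondary ambiguity inside 10.1. Section 10.1 is probably the intended definition, but the plan does not say so for escalation.

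**What to change.** In 9.3:

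- Replace the DLT sentence with *DLT is defined in section 10.1*.
- Replace the five-patient expansion with the rule in the Dose-escalation Rules (three more).
- Keep the significant-hazard clause.

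In 10.1:

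- Run the DLT window from the start of SRT through the 1-month post-SRT visit, and end the wait before escalation at that same visit. Section 10.2 already implies one month of observation after SRT between groups.
- Add an item for any other grade 4 toxicity at least possibly related to SRT. This covers kidney. Keep (e) and (f).
- As a secondary edit, state in (a) that isolated enzyme elevations are covered by (d), and exclude them from the new item so that it does not readmit the short rises that (d) screens out.

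The cost is wording in two sections and a clinical decision to confirm the list. No research-only tests are needed, and the planned maximum of 28 patients does not change. Compared with 10.1 now, somewhat more events count, so expansions may be more frequent and escalation slightly more cautious. Compared with 9.3 now, three kinds of event leave the formal count: unrelated grade 4 events, those first seen after the 1-month visit, and short isolated enzyme rises. Item (e) events enter it. The hazard clause remains the safeguard for what leaves.

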## **Section 3.0 Eligibility Criteria**

### **3.1 Inclusion Criteria:**

Patients must meet all the following criteria

- 3.1.1 Male or female patients  $\geq$  19 years of age
- 3.1.2 A life expectancy of at least 12 weeks with a Karnofsky performance status  $\geq$  60% (Appendix V)
- 3.1.3 Histologically or cytologically documented HCC
- 3.1.4 The target lesion can be accurately measured in at least one dimension according to RECIST and must have a maximum tumor diameter of  $\leq$  8 cm

- 3.1.5 Previous systemic chemotherapy or non-radiation local therapy (such as surgery, hepatic arterial therapy, chemoembolization, radiofrequency ablation, percutaneous ethanol injection or cryoablation) is allowed. Local therapy must be completed at least 6 weeks prior to the baseline scan.
- 3.1.6 Cirrhotic status of Child-Pugh class A and B (Appendix I)
- 3.1.7 Platelet count  $\geq 60 \times 10^9/L$ , Hemoglobin  $\geq 8.5$  g/dL, WBC  $\geq 2000/\mu L$
- 3.1.8 International normalized ratio (INR) must be  $\leq 2.3$ . Patients who are being therapeutically anticoagulated with an agent such as Coumadin or heparin will be allowed to participate provided that no prior evidence of underlying abnormality in these parameters (PT, PTT, INR) exists.
- 3.1.9 Must be aware of the neoplastic nature of his/her disease and willingly provide written, informed consent after being informed of the procedure to be followed, the experimental nature of the therapy, alternatives, potential benefits, side-effects, risks and discomforts.

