#### 5.5 Dose Modifications:

Radiation therapy will be held if the AGC is  $< 500/\mu\text{L}$  and/or the platelets are  $< 50,000/\mu\text{L}$ . Upon recovery of the AGC to  $\geq 500/\mu\text{L}$  and platelets to  $> 50,000/\mu\text{L}$ , radiation therapy will resume at the full planned daily dose.

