### 5.6 Criteria for removal of patients from study

#### 5.6.1 Disease progression

#### 5.6.2 Study closure

#### 5.6.3 Any dose limiting toxicity (defined at section 10.1)

#### 5.6.4 Patient decision to withdraw from the study, or

In the judgment of the investigator, further treatment would not be in the best interest of the patient.

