#### Dose-escalation Rules

A standard cohort escalation design will be employed to evaluate 3 dose levels of SRT. Three patients will initially be treated at each dose level. A minimum of 1 month of observation after surgery is required in all 3 patients before escalation is initiated.

At the second dose level, 3 patients are entered. If:

0/3 have DLT	then the third dose level is investigated.
2/3 have DLT	then the MTD is exceeded at the second dose level. De-escalation of SRT to the first dose level will be considered.
1/3 have DLT	then 3 additional patients are entered. If none of the additional patients develop DLT, then the third dose will be investigated. Otherwise, the MTD is exceeded at the second dose level. De-escalation of SRT will be considered.

At the third dose level, 3 patients are entered. If:

0/3 have DLT	then the fourth dose level is investigated.
2/3 have DLT	then the MTD is exceeded at the third dose level. The second dose level will be expanded to a total of 6 patients (if only 3 patients had been treated).
1/3 have DLT	then 3 additional patients are entered. If none of the additional patients develop DLT, then the fourth dose will be investigated. Otherwise, the MTD is exceeded at the third dose level.

At the fourth dose level, 3 patients are entered. If:

0-1/3 have DLT	then 3 additional patients are entered. If at most 1 of 6 patients develops DLT, then the fourth dose will be declared the MTD. Otherwise, the MTD is exceeded and the third dose level will be expanded to a total of 6 patients (if only 3 patients had been treated).
2/3 have DLT	then the MTD is exceeded and the third dose level will be expanded to a total of 6 patients (if only 3 patients had been treated).

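### The platelet recovery level of 80 in DLT item (e) conflicts with the 50,000/µL resume level in 5.5, and a patient back at a baseline of 60–79 cannot meet it

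*Combined protocol and SAP*

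**What the plan says.** Section 10.1 (Endpoints) lists the dose-limiting toxicities. Item (e) begins with "any adverse event requiring interruption of therapy by" two weeks or more, given as 14 calendar days. It excludes a patient's own wish to stop, then adds: "It does include failure for thrombocytopenia to improve to a level of 80 requiring interruption of therapy". No unit follows the 80. Item (c) separately makes grade 4 or 5 thrombocytopenia a DLT.

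Section 5.5 (Dose Modifications) holds SRT when platelets are below 50,000/µL. Once they are above that level, and the granulocyte count has also recovered, "radiation therapy will resume at the full planned daily dose".

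Section 3.1.7 sets the platelet floor for entry at 60 × 10^9/L, and 3.1.6 admits Child-Pugh A and B cirrhosis. Section 5.6.3 makes any DLT a reason for removal from study and refers to 10.1 for the definition.

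**The concern.** The same patient can meet three platelet levels: one to enter, one to resume treatment and one to count as recovered under the DLT definition. Nothing in the protocol links the third to the other two. Section 5.5 ends a hold above 50,000/µL, while item (e) implies that an interruption can still be required until 80 is reached. For counts between the two, the sections disagree on whether therapy should be interrupted, and so on whether the 14-day rule can be met.

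Two things are at stake. First, a patient who entered at 60–79 could be back at baseline, and back on full-dose SRT under 5.5, while short of the recovery level in the DLT definition. Secondly, DLT counts drive escalation in cohorts of three, so a single classification matters.

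**Working it through.** The plan gives no calculated figure for this point, so there is nothing to reproduce. The check sets the levels side by side.

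**1. Common unit.** One litre is 10^6 µL, so 50,000/µL × 10^6 = 50 × 10^9/L. The 80 is assumed to be in the unit of 3.1.7.

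| Section | Purpose | Platelets (10^9/L) |
|---|---|---|
| 3.1.7 | entry | 60 or more |
| 5.5 | hold SRT | below 50 |
| 5.5 | resume at full dose | above 50 |
| 10.1(e) | recovery level in the DLT definition | 80 (unit assumed) |

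**2. A held patient, followed to day 14 of the hold.** Assume that the event is at least possibly SRT-related and never grade 4, that granulocytes are adequate and that fractions remain.

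| Best count by day 14 | Under 5.5 | Under (e), if 80 ends the interruption | Agree? |
|---|---|---|---|
| not above 50 | still on hold | 14-day interruption: DLT | yes |
| above 50, below 80 | full dose resumed; no interruption required | interruption still required: DLT | no |
| 80 or more | resumed | recovered: no DLT | yes |

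The conflict lies entirely in the middle row.

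**3. Return to baseline.** Let the entry count be B, from 60 to 79. A patient fully back at baseline falls short of the recovery level by 80 − B: 80 − 60 = 20 at the bottom of the range and 80 − 79 = 1 at the top. For every such patient, complete recovery is not enough.

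**4. How narrow the case is.** Grade 4 or 5 thrombocytopenia is already a DLT under (c). A related hold of 14 days or more below the 5.5 level is a DLT whichever level is used. The event must also occur during five fractions given within two weeks, since a low count found after the last fraction leaves no therapy to interrupt. The documents do not say how often platelets would fall this way.

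**5. What one classification does.** Under the Dose-escalation Rules at level II, moving from 0/3 to 1/3 adds three patients. Moving from 1/3 to 2/3 means: "then the MTD is exceeded at the second dose level. De-escalation of SRT to the first dose level will be considered". Among the three added patients, one DLT is enough to stop escalation: "If none of the additional patients develop DLT, then the third dose will be investigated".

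**6. Whether a hold can be triggered on schedule.** Section 7.1 lists the CBC at baseline, after SRT and at follow-up. Appendix II lists it at screening, 1–7 days after implantation, at SRT planning, and at 1 and 3 months after SRT; its columns for the start and end of SRT are empty for CBC. No scheduled count therefore falls between the start and end of SRT, so the 5.5 hold depends on an unscheduled test.

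**The case against.** The strongest reply is that item (e) already contains its own limits. It concerns interruptions of 14 days or more, and the 80 sentence itself ends by requiring an interruption. Once 5.5 has restarted SRT above 50,000/µL, no interruption is required, so the 80 never comes into play. Section 9.3 points the same way: after grade 1 to 3 toxicity "the investigator may elect to continue the treatment with careful monitoring", and grade 4 or greater is what it calls a DLT. Thresholds for entry, holding and DLT serve different purposes and need not be equal. The missing unit is obvious from 3.1.7.

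Much of this stands. A reader might infer that 80 is a free-standing test, so that any held patient who fails to reach it has a DLT however short the hold. The documents do not support that, because it drops both the 14-day condition and the requirement of an interruption. The missing unit is a small matter, and different levels for different purposes are not in themselves a fault.

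The conflict remains all the same. If 5.5 decides when an interruption is required, the 80 has no effect on a 5.5 hold and could matter only if an investigator interrupts at a higher count by discretion. If 80 decides, it contradicts 5.5. No section says which prevails. Section 9.3 does not settle it, because its DLT statement has no platelet recovery level and 5.6.3 refers to 10.1 for the definition.

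**Conclusion.** The point holds as a minor conflict between sections. The 80 in 10.1(e) does not fit the resume level in 5.5, and a patient who entered at 60–79 and has returned to baseline cannot meet it. This assumes that the 80 is in 10^9/L and that the sentence is an instance of the 14-day rule.

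No numerical effect on the trial is claimed. A reader might infer a large shift in the chance of escalating by supposing one affected patient and counting the DLT or not. That would show only what any single reclassified DLT does in cohorts of three; it would not measure this defect, whose frequency is not in the documents. A reader might also infer that the ambiguity lets someone choose the classification once the cohort result is known. Nothing in the documents suggests this, and 9.3 provides for weekly review of all patients and audit of adverse events by a clinician outside the trial.

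The missing CBC is a related, secondary gap: the hold in 5.5 has no scheduled count to trigger it.

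**What to change.** In 10.1(e), replace the 80 sentence with: *It includes failure of platelets to recover to above 50,000/µL within 14 days of the start of a hold.* This gives the level a unit and a time limit and makes it agree with 5.5. It also fits the 30-day DLT window: a hold that starts by day 14 of a two-week course reaches its limit by day 14 + 14 = 28. The cost is one sentence. If the sponsor meant 80 as a stricter criterion, the change gives that up for patients who recover only to between 50 and 80.

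In 7.1 and Appendix II, add a CBC at the weekly visit during SRT that 9.3 already describes. With SRT given within two weeks, this means one or two extra blood draws per patient at an existing visit. The count guides a treatment hold, so it is not a research-only procedure of the kind that 5.3 rules out.
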